10.3 D-dimer

D-dimer will be measured at Beth Israel Deaconess Medical Center at baseline and end of treatment . Relative change in D-dimer will be assessed for each arm.

10.4 TFMP levels and thrombotic risk

Absolute TFMP levels will be measured at baseline and 56 days. A correlation between TFMP and thrombotic risk will be investigated according to randomization arm (see Section 13.2).

10.5 Quality of Life

Quality of Life (QOL) will be assesses using EORTC QLQ-30 which is an internationally validated and widely utilized questionnaire (Appendix D).⁵⁷ Scoring is based on responses to 30 questions dealing with functional quality (such as cognitive, physical, and emotional) as well as symptom burden (such as fatigue, nausea, and sleep). The questionnaire will be completed at baseline visit and at the end of study assessment. For non-English speaking participants, the questionnaire will be completed with a translator.

10.6 Overall Survival

Will be recorded every 6 months.

10.7 Definitions

Evaluable for toxicity. All participants who receive at least one dose of study treatment will be evaluable for toxicity from the time of their first treatment.

Evaluable for VTE and D-dimer endpoints. Only those participants who undergo an evaluation for VTE after day 1 (either diagnosed with VTE) or completed at least 1 cycle of treatment (along with requisite off treatment evaluation) will be considered evaluable for VTE and D-dimer endpoints.

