5.4 Duration of Follow Up

Following completion of treatment, only the cause and date of death will be recorded. Participants removed from study for unacceptable adverse events will be followed until resolution or stabilization of the adverse event. Participants removed from active treatment will be followed for survival.

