9 STUDY CALENDAR

Baseline evaluations are to be conducted within 15 days prior to start of protocol therapy.

All assessments must be performed prior to administration of any study medication. All study assessments and medications should be administered within \pm 7 days of the protocol-specified date, unless otherwise noted.

Event/Procedure	Screening/ Pre- treatment visit	Day 1 (C1D1)	Day 29 (C2D1)	Day 56 or End of Study Treatment	Survival Assessment
Day Range	-15 to 0		+ 2 days	+ 5 days	Q6 months
History Assessments	Х				
Informed Consent	Х				
Inclusion/Exclusion Criteria	Х				
Medical History	Х		х	х	
ECOG Performance Status Score	х		х	х	
Concomitant medication review	Х		Х	х	
Treatment allocation ⁶	Х				
Dispense study drug		х	Х		
Drug Diary Collection ³			х	х	
Safety Assessments					
Physical examination including vital signs	Х		х	х	
Height and Weight	Х				
AE/SAE assessment	Х		х	х	
Assessment of signs and symptoms of VTE and bleeding	х		х	х	
Laboratory Tests					
Complete blood count with diff	Х	х	х	Х	
РТ/РТТ	Х				
Creatinine	Х		Х		
AST/ALT	Х		Х		
Total bilirubin	Х				
Urine HCG ⁴	Х				
Correlative plasma samples (all sites) ¹		x		х	
Correlative plasma samples (BIDMC only)		X5		х	
Imaging					
Bilateral lower extremity ultrasound				х	
Quality of Life Survey ²		Х		х	

CONFIDENTIAL This document is confidential. Do not disclose or use except as authorized. ¹Correlative lab instructions (TFMP) provided in Appendix E
²QOL survey provided in Appendix D
³Drug Diary
⁴If applicable
⁵Optional correlative labs to be drawn at time 0 and 4 hours (see section 7.1)
⁶Phase II treatment allocation is by sequential dosing cohort, Phase III allocation is by randomization

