10 MEASUREMENT OF EFFECT

10.1 Venous Thromboembolism (VTE)

Cumulative incidence of venous thromboembolic events at 56 days (+/- 7 day windows) is the primary endpoint. *The composite endpoint includes any symptomatic proximal or distal lower extremity DVT, symptomatic pulmonary embolism or fatal PE diagnosed by autopsy, asymptomatic proximal DVT diagnosed by screening compression ultrasound.* All other venous or arterial events will be recorded and analyzed as secondary endpoints.

Patients presenting with symptoms compatible with DVT and/or PE will undergo radiographic imaging with either compression ultrasound, VQ lung scan, or spiral CT. Confirmed episodes of VTE will be managed by the treating physician per standard of practice.

Presence of any of the following will be considered diagnostic for a VTE:

- New non-compressibility of lower extremity deep venous segments by compression ultrasound. Distal lower extremity thrombus (lower than popliteal vein) qualifies for primary VTE endpoint only if symptomatic. All proximal thrombi qualify as primary study endpoint if identified by screening ultrasound or are symptomatic.
- Intraluminal defects in two or more views on pulmonary angiography
- Sudden contrast cut-off of one or more vessels greater than 2.5 mm in diameter on a pulmonary angiogram
- A high probability VQ lung scan showing one or more segmental perfusion defects with corresponding normal ventilation (mismatch defect)

• Abnormal spiral CT showing thrombus in pulmonary vessels (subsegmental or larger) Note: intrabdominal thrombus related to tumor compression is not considered a VTE endpoint

Other VTE

Those VTE that do not qualify for the primary endpoint such as asymptomatic distal extremity deep vein thrombosis, asymptomatic pulmonary emboli diagnosed by CT, central line-associated thrombus will be recorded and analysed as secondary endpoints.

Response Review

An independent adjudication of VTE qualifying for the primary outcome will be performed. The review committee will be comprised of two independent hematologists and a radiologist. The committee will review the medical records and radiology report for all VTE that qualify for the primary VTE endpoint. In cases where committee feels that the radiology reports or medical records are equivocal then the primary radiology images will be reviewed by an independent radiologist for adjudication.

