14.1 Study Design/Endpoints

- 14.1.1 The primary endpoint of the Phase II trial is to investigate whether isoquercetin significantly reduces d-dimer values in cancer patients. D-dimer is a readily available biomarker used clinically in the prediction and diagnosis of VTE. In cancer cohorts, the D-dimer has modest specificity for predicting symptomatic thrombosis.⁵⁸ However, D-dimer remains the most validated surrogate marker of thrombin generation in vivo and symptomatic VTE.
 - 14.1.1.1 **Study Design**: The trial is a sequential cohort study of isoquercetin 500 mg and 1000 mg daily.
 - 14.1.1.2 Randomization: Patients will not be randomized.
 - 14.1.1.3 Accrual: Anticipated accrual is 10 patients per month across all study sites.

14.1.1.4 Sample Size Justification: Plasma D-dimer levels typically decrease at least 20% following the initiation of anticoagulation.⁵⁹ The sample size is based on a paired t-test of D-dimer concentrations measured on day 1 and end of treatment, to be performed separately for each arm. In the recently completed MicroTEC study, the median baseline D-dimer concentration for all cancer patients enrolled was 815 ug/L.⁴⁷ Based on an estimated standard deviation of 0.3 for the ratio of the D-dimer levels at day 56 over the D-dimer levels at day 1, a total of 26 subjects are needed per arm for a 90% power to declare the reduction significant if the true concentration at end of treatment is reduced by 20% in each isoquercetin arm (one-sided alpha 0.05). Estimated death or dropout of 5% prior to 56 days, the sample size will be increased to a total of total 30 per arm (onesided alpha 0.05). With 30 eligible patients per dose level, there is greater than 60% power to detect an unacceptable attributable grade 3 or 4 rate of 15% at 56 days using a one-sided 10% level exact binomial test in each dose level. (see table below)

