- 14.1.2 The primary aim of the **phase III trial** is determine whether isoquercetin reduces the cumulative incidence of symptomatic or proximal VTE in cancer patients at 56 days.
 - 14.1.2.1 **Study design:** The trial is a randomized, placebo-controlled, doubleblinded phase III trial. Study subjects are randomized to placebo or isoquercetin. The structure of the study matches the phase II study, the central differences being that VTE is the primary endpoint and a single isoquercetin arm is compared to placebo.
 - 14.1.2.2 **Randomization:** Central randomization (1:1) will be performed by QACT Office at DF/HCC and stratified by cancer diagnosis and institutions.
 - 14.1.2.3 Accrual: Anticipated accrual is 20 patients per month across all sites.

14.1.2.4 Sample size justification:

The overall incidence of thrombosis in cancer populations varies between 2-40% based on histology, stage, chemotherapeutics, additional risk factors and mode of surveillance (imaging or symptomatic events). The overall cumulative incidence of VTE in recently conducted MicroTEC study with similar eligibility criteria and study design was 11.3%. The estimate of isoquercetin benefit is based on data from primary thromboprophylaxis trials that typically achieve VTE rates of 4% or less.^{60,61} Based on the estimated VTE rates of 11% in the placebo and 4% isoquercetin arms, a total of 281 isoquercetin-treated subjects and 281 placebo-treated subjects would be required to reject the null hypothesis that the failure rates for experimental and control subjects are equal with probability (power) 0.85. The 1-sided type I error probability associated with this test of this null hypothesis is 0.025. In order to adjust for death or dropout of 5% prior to 56 days, the sample size is increased by an additional 28 patients. We plan an interim analysis for efficacy or futility after 50% of patients have been randomized that will be guided by O'Brien-Fleming boundaries. This will require an additional increase in sample size of 5% or 28 patients. Therefore, we plan to enroll a total of 618 patients. A total of 30 patients enrolled in the phase II trial will be included in the total accrual target and final VTE endpoint analysis.

14.1.3 Primary endpoint analysis will be performed on an intention to treat basis following randomization for all patients who undergo baseline assessment for the presence of VTE and at least one dose of study medication. The cumulative incidence of VTE

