14.3 Reporting and Exclusions

- 14.3.1 **Evaluation of toxicity.** All participants who received a dose of study drug will be assessed for toxicity.
- 14.3.2 **Evaluation of response.** All participants included in the study must be assessed for response to treatment, even if there are major protocol treatment deviations or if they are ineligible. For the phase II study, primary endpoint analysis will be performed on an intention to treat basis for patients who undergo randomization and completed both the baseline and day 56 blood draw. For the phase III study, primary endpoint analysis will be performed on an intention for all patients who undergo baseline assessment for the presence of VTE.

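### Phase III VTE analysis: 30 non-randomised phase II patients are pooled in, VTE after an early treatment stop is only partly captured to day 56, and 10.7 conflicts with intention to treat

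*Combined protocol and SAP*

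**What the plan says.** **Endpoint.** Section 10.1: "Cumulative incidence of venous thromboembolic events at 56 days (+/- 7 day windows) is the primary endpoint". Section 14.1.3 analyses it by competing risks with the Gray test. It does not name the competing event or say when a patient is censored.

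**Phase II patients.** Section 14.1.2.4: "A total of 30 patients enrolled in the phase II trial will be included in the total accrual target and final VTE endpoint analysis". For phase II, section 14.1.1.2 says: "Patients will not be randomized".

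**Follow-up.** Meeting any criterion in 5.3 removes the patient from study (5.5). The only ultrasound in the calendar falls in the column "Day 56 or End of Study Treatment". Section 5.4 continues: "Following completion of treatment, only the cause and date of death will be recorded". Patients with symptoms of VTE are imaged, and qualifying events are adjudicated (10.1). Serious adverse events are reportable to 30 days after the last dose (11.3.1, 11.4.1), and 11.9 uses the same 30 days for all adverse events. Section 6 collects adverse events only up to the final study visit.

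**Analysis set.** Three definitions stand side by side:
- 10.7, evaluable for VTE: "Only those participants who undergo an evaluation for VTE after day 1 (either diagnosed with VTE) or completed at least 1 cycle of treatment", with the off-treatment evaluation.
- 14.1.3, intention to treat: "for all patients who undergo baseline assessment for the presence of VTE and at least one dose of study medication".
- 14.3.2: "primary endpoint analysis will be performed on an intention for all patients who undergo baseline assessment for the presence of VTE". The same section requires every participant to be assessed despite major deviations or ineligibility.

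**The concern.** Three features weaken the comparison that randomisation is meant to protect.

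1. The 30 phase II patients all received isoquercetin, were enrolled earlier and had no concurrent placebo group. Putting them in the final VTE analysis mixes a historical group into a randomised contrast, and their own VTE rate then moves the result.
2. A patient who stops treatment early may have VTE between the stop and day 56. No passage makes that period part of endpoint collection, and the analyst is not told whether to censor the patient or treat the patient as VTE-free.
3. The conditions in 10.7 all arise after randomisation. An early VTE is kept, while a patient who dies or leaves in cycle 1 with no VTE evaluation is dropped. The competing-risk analysis needs those early deaths.

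At stake are the error rate of a one-sided test for benefit at 0.025, some power, and endpoint data that are hard to recover later.

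**Working it through.** **1. The plan's own figure.** Inputs from 14.1.2.4: 11% versus 4%, one-sided 0.025, power 0.85, 1:1. With mean rate 0.075 and difference 0.07:

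n = [1.960·√(2·0.075·0.925) + 1.036·√(0.11·0.89 + 0.04·0.96)]² / 0.07² = 253 per arm.

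The continuity correction, n/4·[1 + √(1 + 4/(0.07n))]², gives 281, as stated. Then 562 + 28 + 28 = 618. Without the 30 phase II patients, 618 − 30 = 588, or 294 per arm.

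**2. Pooling the 30.** Assume that they join the drug arm and that both randomised arms have 11% VTE. The expected drug-arm rate is (294·0.11 + 30·r)/324, where r is the assumed phase II rate. The last column is the one-sided rejection rate for efficacy of a pooled two-proportion z test.

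| r | Expected drug rate | Rejection |
|---|---|---|
| 11% | 11.0% | 2.5% |
| 4% | 10.4% | 4.4–4.6% |
| 20% | 11.8% | 1.1% |

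The range in the second row covers 279 to 309 patients per arm.

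**3. Reach of the 30-day window.** A stop on day d is covered to day d + 30, so stops before about day 26 (56 − 30) are not covered to day 56. If stop days are spread evenly, the window covers (26·30 + 30²/2)/(56²/2) = 1230/1568 = 78% of the time between stop and day 56. It adds no ultrasound, so asymptomatic proximal DVT is outside it.

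**4. Effect of 10.7.** The only loss figure in the plan is 5% death or dropout by day 56. At a constant rate, half of it (2.5%, about 15 of 588) falls in cycle 1. Take 294 per arm, 11% VTE in both, and exclusions only among patients without VTE. The expected rate is then 0.11/(1 − loss). Differences between arms are assumptions.

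| Loss, placebo / drug | Expected rates | Rejection for efficacy |
|---|---|---|
| 5% / 5% | 11.6% / 11.6% | 2.5% |
| 5% / 2.5% | 11.6% / 11.3% | 3.2% |
| 2.5% / 5% | 11.3% / 11.6% | 1.9% |
| 5% / 10% | 11.6% / 12.2% | 1.4% |
| 5% / 15% | 11.6% / 12.9% | 0.7% |

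A one-point gap (2.5% and 3.5%) gives 2.8% if placebo loses more and 2.2% if drug does. The last two rows are stress tests.

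**5. Handling of early stoppers.** This was simulated with a Gray-type test: 294 per arm, exponential VTE and death times, 5% deaths by day 56, uniform stop times, 24,000 null trials per case (standard error 0.10 points).
- Censored at stop, stopping unrelated to VTE: error 2.5%. With equal stopping, power is 0.91 with no stopping, 0.90 at 5% and 0.88 at 20%.
- Carried as VTE-free, with stopping 2.5% or 5% on placebo against 5% or 7.5% on drug: error 2.7–2.9% with no later capture and 2.5–2.6% with full 30-day capture. More stopping on drug favours drug here, the opposite of 10.7.
- Censored at stop, same imbalances, stoppers at 2 to 3 times the VTE hazard: error 2.5–3.1%.

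**The case against.** The case on the other side is substantial. Section 14.3.2 says all participants must be assessed whatever their deviations, and no analysis in section 14 uses the evaluable set, so intention to treat is the better reading. The parenthesis in 10.7 is incomplete. If a negative evaluation qualifies, only patients with no evaluation at all are lost. Early stoppers are due an end-of-treatment visit with ultrasound, and a competing-risk analysis ordinarily censors at last follow-up. Most of this stands, and it limits the size of points 2 and 3. It does not remove them: 10.7 is not set aside, the safety window is not tied to the endpoint, and the censoring date is unstated.

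Three stronger readings are tempting, and the documents do not support them:
- That 10.7 inflates false claims of benefit. The test is one-sided for benefit, so this needs more exclusions on placebo. More exclusions on drug lower the error. No loss rates by arm are given, and double-blinding should favour similar losses.
- That no VTE is captured after an early stop. Imaging of symptomatic patients and the 30-day reporting window would catch part of the symptomatic events.
- That pooling the 30 favours the drug. The direction depends on their own VTE rate, which the documents cannot give.

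The at-least-one-dose condition in 14.1.3 is a secondary matter in a blinded trial.

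**Conclusion.** The concern holds in a limited form, and the plan should be changed before phase III. Pooling the 30 phase II patients is the clearest fault, because the final comparison is then not purely randomised. With assumed phase II rates of 4% to 20%, its one-sided error runs from about 4.5% down to 1.1%, and stays at 2.5% only if their rate matches that of the randomised patients. The gap after an early stop and the conflict between 10.7 and section 14 are real but smaller. With equal losses, or censoring at stop unrelated to VTE risk, type I error holds and the cost is some events and power. With unequal losses near the documented 5%, the one-sided error lies between about 1.9% and 3.3%, in a direction that depends on which arm loses more and which rule is applied. All differences between arms, stop times and hazard ratios here are assumptions. The sample size of 281 per arm is not in dispute.

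**What to change.** Section 5 already plans an amendment before phase III, and these changes can go into it.

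1. **One primary set.** All patients randomised in phase III, analysed as randomised, with death without VTE as the competing event. State that 10.7 does not define this set, and use the same wording in 14.1.3 and 14.3.2. The dose condition may stay or go, provided that one wording is used.
2. **Phase II patients.** Report the 30 separately or in a labelled supplementary analysis, and restate the randomised numbers. With 588 randomised, 294 per arm becomes 279 after 5% loss, with one-sided Fisher power 0.862 (0.864 at the plan's 281). The plan without its interim allowance is 562 + 28 = 590, so 588 does not contain the 28 patients added for the interim. Either state the power with the interim at 588, or randomise the full 618, which costs 30 more patients.
3. **VTE follow-up.** Reconcile 5.4, 5.5, 6, 11.9 and the calendar with the 56-day endpoint, so that VTE status is collected to day 56 by visit, contact or record review after an early stop, and qualifying events go to the 10.1 adjudication. Treatment-stopping rules are unchanged. The cost is up to 8 weeks of contact or record review per early stopper. Asymptomatic DVT arising after an early scan may still be missed.
4. **Censoring.** Censor a living patient with unknown status at the last date on which VTE status is known, and do not carry that patient as VTE-free. Add a sensitivity analysis for informative stopping, for example 1, 2 and 3 times the arm's VTE hazard in stoppers with unknown status.

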11 ADVERSE EVENT REPORTING REQUIREMENTS

11.1 Definitions

11.1.1 Adverse Event (AE)

An adverse event (AE) is any undesirable sign, symptom or medical condition or experience that develops or worsens in severity after starting the first dose of study treatment or any procedure specified in the protocol, even if the event is not considered to be related to the study.

Abnormal laboratory values or diagnostic test results constitute adverse events only if they induce clinical signs or symptoms or require treatment or further diagnostic tests.

11.1.2 Serious adverse event (SAE)

A serious adverse event (SAE) is any adverse event, occurring at any dose and regardless of causality that:

- Results in death
- Is life-threatening. Life-threatening means that the person was at immediate risk of death from the reaction as it occurred, i.e., it does not include a reaction which hypothetically might have caused death had it occurred in a more severe form.
- Requires or prolongs inpatient hospitalization (i.e., the event required at least a 24-hour hospitalization or prolonged a hospitalization beyond the expected length of stay). Hospitalizations will not be considered SAEs unless they meet the criteria specified in the table in Section 11.3.2: DF/HCC Reportable AEs. Hospitalization admissions and/or surgical operations scheduled to occur during the study period, but planned prior to study entry are not considered SAEs if the illness or disease existed before the person was enrolled in the trial, provided that it did not deteriorate in an unexpected manner during the trial (e.g., surgery performed earlier than planned).
- Results in persistent or significant disability/incapacity. Disability is defined as a substantial disruption of a person's ability to conduct normal life functions.
- Is a congenital anomaly or birth defect; or
- Is an important medical event when, based upon appropriate medical judgment, it may jeopardize the participant and require medical or surgical intervention to prevent one of the outcomes listed above. Examples of such medical events include allergic bronchospasm requiring intensive treatment in an emergency room or at home; blood dyscrasias or convulsions that do

not result in inpatient hospitalization, or the development of drug dependency or drug abuse.

Events **not** considered to be serious adverse events are hospitalizations for: routine treatment or monitoring of the studied indication, not associated with any deterioration in condition, or for elective procedures elective or pre-planned treatment for a pre-existing condition that did not worsen. Emergency outpatient treatment for an event not fulfilling the serious criteria outlined above and not resulting in inpatient admission respite care.

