11.3.2 DF/HCC Expedited Reporting Guidelines

Investigative sites within DF/HCC and DF/PCC will report SAEs directly to the DFCI Office for Human Research Studies (OHRS) per the DFCI IRB reporting policy.

Other investigative sites will report SAEs to their respective IRB according to the local IRB's policies and procedures in reporting adverse events. A copy of the submitted institutional SAE form should be forwarded to the Overall PI within the timeframes detailed in the table below.

	DF/HCC Reportable AEs					
Attribution	Gr. 2 & 3 AE Expected	Gr. 2 & 3 AE Unexpected	Gr. 4 AE Expected	Gr. 4 AE Unexpected	Gr. 5 AE Expected or Unexpected	
Unrelated Unlikely	Not required	Not required	5 calendar days [#]	5 calendar days	24 business hours*	
Possible Probable Definite	Not required	5 calendar days	5 calendar days [#]	5 calendar days	24 business hours*	

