11.4 Reporting to the Study Sponsor

11.4.1 Serious Adverse Event Reporting

All serious adverse events that occur after the initial dose of study treatment, during treatment, or within 30 days of the last dose of treatment must be reported to the DF/HCC Overall Principal Investigator on the local institutional SAE form. This includes events meeting the criteria outlined in Section 10.1.2, as well as the following:

- Grade 2 (moderate) and Grade 3 (severe) Events Only events that are unexpected and possibly, probably or definitely related/associated with the intervention.
- All Grade 4 (life-threatening or disabling) Events Unless expected AND specifically listed in the protocol as not requiring reporting.

• All Grade 5 (fatal) Events – When the participant is enrolled and actively participating in the trial OR when the event occurs within 30 days of the last study intervention.

Note: If the participant is in long term follow up, report the death at the time of continuing review.

Participating investigators must report each serious adverse event to the DF/HCC Overall Principal Investigator within 1 business day of learning of the occurrence. In the event that the participating investigator does not become aware of the serious adverse event immediately (e.g., participant sought treatment elsewhere), the participating investigator is to report the event within 24 hours after learning of it and document the time of his or her first awareness of the adverse event. In the case of a medical emergency which may require unblinding, contact the Overall Principal Investigator. Report serious adverse events by telephone, email or facsimile to:

Within the following 24-48 hours, the participating investigator must provide follow-up information on the serious adverse event. Follow-up information should describe whether the event has resolved or continues, if and how the event was treated, and whether the participant will continue or discontinue study participation.

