12.2 Safety Meetings

During the phase II portion of the study, the DF/HCC Data and Safety Monitoring Committee (DSMC) will review and monitor toxicity and accrual data from this study. The committee is composed of clinical specialists with experience in oncology and who have no direct relationship with the study. Information that raises any questions about participant safety will be addressed with the Overall PI and study team.

The DSMC will review each protocol up to four times a year or more often if required to review toxicity and accrual data. Information to be provided to the committee may include: up-to-date participant accrual; current dose level information; DLT information; all grade 2 or higher unexpected adverse events that have been reported; summary of all deaths occurring with 30 days of intervention for Phase I or II protocols; for gene therapy protocols, summary of all deaths while being treated and during active follow-up; any response information; audit results, and a summary provided by the study team. Other information (e.g. scans, laboratory values) will be provided upon request.

The DF/HCC Data and Safety Monitoring Board (DSMB) will review and monitor study progress, toxicity, safety and other data from this trial during the Phase III portion of the study. The board is chaired by a medical oncologist from outside of DF/HCC and has external and internal representation. Information that raises any questions about participant safety or protocol performance will be addressed with the Principal Investigator, statistician and study team members. Should any major concerns arise, the DSMB will offer recommendations regarding whether or not to suspend the trial.

The DSMB will meet twice a year to review accrual, toxicity, response and reporting information. A DSMB review will also be triggered if the number of toxicity events (possible or definite grade 3 or 4 toxicity or major hemorrhage) prompts an automatic enrollment hold within either cohort or prior the next dosing cohort. Information to be provided to the DSMB may include: participant accrual, treatment regimen information, adverse events and serious adverse events reported by category, summary of any deaths on study, audit results, and a summary provided by the study team. Other information (e.g. scans, laboratory values) will be provided upon request.

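### Section 11.1.2 defines serious events without regard to cause, then counts a hospitalization as serious only if it passes a table sorted by attribution and expectedness

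*Combined protocol and SAP*

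**What the plan says.** Section 11.1.2 opens: "A serious adverse event (SAE) is any adverse event, occurring at any dose and regardless of causality that" leads to one of six listed outcomes. The third is hospitalization: "Requires or prolongs inpatient hospitalization (i.e., the event required at least a 24-hour hospitalization or prolonged a hospitalization beyond the expected length of stay". The next sentence of that bullet restricts it: "Hospitalizations will not be considered SAEs unless they meet the criteria specified in the table in Section 11.3.2: DF/HCC Reportable AEs". The section also excludes planned and elective admissions, which is a separate matter and not in dispute here.

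The table in Section 11.3.2 gives deadlines for expedited reporting. Its rows are attribution (unrelated or unlikely; possible, probable or definite). Its columns are grade by expectedness, for example "Gr. 2 & 3 AE Unexpected". The first row begins "Unrelated Unlikely Not required Not required 5 calendar days".

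Section 11.4.1 then relies on the definition. "All serious adverse events that occur after the initial dose of study treatment, during treatment, or within 30 days of the last dose" must go to the Overall Principal Investigator on the SAE form, within 1 business day. Section 11.4.2 sends non-serious events to the same person on toxicity case report forms. Section 11.5 has DF/HCC sites send every SAE to the IRB office. Section 12.2 lists, among what the DSMB may receive in phase III, "adverse events and serious adverse events reported by category".

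**The concern.** Seriousness describes what happened to the patient. Attribution and expectedness are judgements that decide how fast an event must be reported and to whom. Section 11.1.2 states the first principle ("occurring at any dose and regardless of causality") and then, for hospitalization alone, lets the second kind of judgement decide whether the event is serious at all.

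Two things are at stake. One is speed: an event classed as non-serious leaves the 1-business-day route. The other is the content of SAE summaries. Patients have advanced cancer and are receiving or about to receive chemotherapy (3.1.1, 3.1.2), so many admissions can reasonably be put down to disease or chemotherapy. In a double-blind, randomized phase III, a count of all unplanned admissions by arm needs no causality judgement. An SAE count that has passed through an attribution filter does.

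**Working it through.** The plan gives no figure to reproduce. The check is a reading of the table, one worked case, and a test of whether the size can be stated.

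**1. The grade 2 and 3 cells of the 11.3.2 table.**

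| Attribution | Expected | Unexpected |
|---|---|---|
| Unrelated, unlikely | not required | not required |
| Possible, probable, definite | not required | 5 calendar days |

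One cell of four lets a grade 2 or 3 hospitalization qualify; three do not. Grade 4 and 5 events carry a deadline under either attribution, apart from the footnote for grade 4 events that the protocol lists as expected and exempt. There is no grade 1 column.

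**2. One event through the text.** Take a grade 3 event, unexpected, with an admission of more than 24 hours, judged unlikely to be related.
- Opening line and hospitalization criterion of 11.1.2: serious.
- Restricting sentence of 11.1.2, with the table: not serious.
- 11.4.1: its additional list of grade 2 and 3 events covers only unexpected and at least possibly related ones, so it does not bring the event back. For the SAE criteria it points to Section 10.1.2, which does not exist, so it cannot settle the conflict.

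In 11.4.1 the grade and attribution conditions add events to the SAE set. In 11.1.2 they remove events from it.

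**3. Delay.** An SAE is due within 1 business day. Under 12.1.2 the adverse event form is due within 10 days of the last day of the cycle, and a cycle is 28 days (Section 5). If the toxicity form of 11.4.2 follows that schedule (an assumption), an event on day 1 may arrive up to 27 + 10 = 37 days later.

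**4. Share affected.** Let u be the proportion of grade 2 and 3 admissions that are unexpected and a the proportion at least possibly related, taken as independent. Then the share excluded is 1 − u × a. The documents give neither input. Under assumed values:

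| u | a = 0.1 | a = 0.3 | a = 0.5 | a = 0.8 |
|---|---|---|---|---|
| 0.5 | 95% | 85% | 75% | 60% |
| 0.7 | 93% | 79% | 65% | 44% |
| 0.9 | 91% | 73% | 55% | 28% |
| 1.0 | 90% | 70% | 50% | 20% |

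The range is 20% to 95%. A majority is excluded only when u × a is below 0.5.

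**5. What uses SAE status.** Section 14 specifies no between-arm analysis of SAEs or hospitalizations. The planned safety comparison is major hemorrhage (14.2), which has its own criteria (10.2). The phase II rules (Section 5, 14.1.1.5) count attributable grade 3 or 4 events, serious or not. What remains is the 1-business-day report and any SAE tabulation.

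**The case against.** The strongest reply is that the events are reclassified, not lost. Section 11.2 puts all adverse events on case report forms, 11.4.2 sends the non-serious ones to the Overall Principal Investigator, and 11.9 follows both kinds to resolution. The DSMB list in 12.2 includes adverse events as well as SAEs, with further information on request. All of this stands. It does not restore the timing, and nothing in the documents says that a non-serious record shows that the patient was admitted.

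Other parts of the reply also stand. The phrase about all serious events in 11.4.1 takes whatever definition 11.1.2 supplies, so the contradiction lies within 11.1.2. The expected list in 6.1.1 is short, and 11.1.5 treats a difference in intensity or frequency as unexpected, so the expectedness column may exclude few admissions; attribution could do most of the excluding. Another criterion, such as an important medical event, may still capture an admission, but only by medical judgement. For grade 2 and 3 events the surviving cell matches the FDA criterion in 11.6, so FDA reporting is largely unaffected.

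A reader might infer two stronger claims. The first is that most grade 2 and 3 hospitalizations disappear from the SAE data. Three cells of four is a count of cells, not of events, and the share cannot be fixed from the documents. The second is that the phase III comparison between arms loses power or is biased. The plan contains no such test. A power figure would need assumed admission rates and an assumption about whether the filter removes drug-caused and background admissions in the same proportion; the documents support neither.

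**Conclusion.** The contradiction in 11.1.2 is certain and rests on the text alone. If sites follow the restricting sentence, grade 2 and 3 hospitalizations that are judged unrelated or unlikely, or that are expected, are handled as non-serious. They remain on toxicity forms, but they miss the 1-business-day report and are not counted in SAE summaries. If sites follow the opening line instead, they are counted. Because the text supports both, sites may differ, and the SAE count would then depend partly on which sentence a site applies.

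The consequence is limited to reporting speed and SAE tabulations, including the SAE part of any DSMB report. Its size in events is unknown. No planned test or toxicity rule changes. The point is worth correcting because the correction is simple and makes the safety data easier to interpret.

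**What to change.** - In 11.1.2, delete the restricting sentence, so that seriousness does not depend on attribution or expectedness. Keep the exclusions for planned and elective admissions.
- In 11.3.2, state that the table governs expedited IRB reporting only.
- In 11.5, tie reporting by DF/HCC sites to that table in place of the present requirement to send every SAE.
- In 11.4.1, change the reference for the SAE criteria from Section 10.1.2 to 11.1.2.
- In 12.2, have the SAE summaries for the DSMB show hospitalizations by arm, without an attribution filter.

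This is a small text amendment. Section 5 already foresees an amendment before phase III that could carry it, though phase II reporting would stay ambiguous until then. The running cost is more SAE forms and more 1-business-day reports to the Overall Principal Investigator for unrelated admissions. If 11.5 is not aligned, DF/HCC sites would also send additional IRB reports.
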